### Secondary objectives:

1. Identify the psychosocial and environmental factors, as well as implementation issues that may mediate or modify the effectiveness of the intervention using qualitative methods. This will include examining:
  - a. voluntary sector readiness to take forward new forms of services;
  - b. the best modes of delivery of telephone support/friendship;
  - c. how volunteers (facilitators) can be supported and retained; and,
  - d. the extent to which fidelity of the intervention is maintained within and across the participating organisations.
2. To determine if there is any lasting impact upon mental wellbeing by repeat measurement with all participants 12 months following baseline measurement
3. To examine whether there is any significant improvement on the physical dimension of the SF36 at 6 months and 12 months following baseline for the intervention arm compared with standard care.
4. To measure the extent of use of health and social care, and community facilities by participants over time to determine whether the intervention is cost effective compared with standard care.

## 3. Trial Design

### Design

Pragmatic two arm parallel group randomised controlled trial with feasibility phase.

### Endpoints

Primary outcome:

1. SF36 Mental Health (MH) dimension (Maruish 2011).

Secondary outcomes:

2. Other dimensions of the SF-36 to measure all aspects of health including physical health (Maruish 2011);
3. Reapplication of the PHQ9 (Spitzer et al, 1995);
4. EQ-5D (for health economic analysis (Brazier et al, 2007);
5. General Perceived Self Efficacy (GSE) Scale (Schwarzer & Jerusalem, 1995);
6. de Jong Gierveld Loneliness scale (de Jong, 1985);
7. A health and social care resource use questionnaire to collect participants' use of health, social care and community services for health economic analysis.

### **Design measures to avoid bias**

The allocation schedule will be concealed through the use of a centralised web-based randomisation service. The trial steering committee (TSC) and trial management group (TMG), including their statisticians will be blind to treatment allocation whilst the trial is ongoing, but the trial manager and participants will not be blinded. Analysis will be by intention-to-treat. Where individuals are lost to follow-up or data is missing, imputation methods will be employed, which will be described in the statistical analysis plan.

### **Duration**

The total duration of the trial, including three recruitment waves and 12 months post randomisation follow-up is three years and one month. The expected duration of involvement of each participant is 12 months.

### **Feasibility assessment**

After the initial set up period of seven months we will run the first wave of recruitment as an internal pilot trial to assess the feasibility of both trial recruitment plans and the proposed intervention. It is assumed that one quarter of potential candidates will be eligible and willing to be randomised. Three phased mail shots will be sent from Sheffield GPs. Based on previous HTA-funded public health research we anticipate 250 respondents (a 5% response rate) out of this strategy. Other recruitment strategies will be instigated alongside the mail shots. We anticipate 90 respondents recruited in the feasibility phase, will be eligible and willing to be randomised. Assuming a 20% loss to follow-up this will allow outcome measurement in 72 individuals to estimate a standard deviation for the primary outcome, SF-36 mental health score, at six months after randomization, the correlation between baseline and six month score and the intra cluster correlation (ICC).

The main risks to trial success to be examined through the feasibility phase are:

1. Insufficient eligible individuals consenting to participate in the trial.
2. The study intervention (telephone friendship groups) will not be delivered effectively due to local implementation issues or inadequate acceptability by participants.

### **Stopping rules**

The TSC will assess the feasibility of the trial seven months after recruitment has commenced, with both recruitment and retention being considered. We will need to recruit 248 people in total to account for an anticipated 20% loss to follow-up at six months (primary outcome assessment time point), giving us 80% power to detect a difference between befriending (n=100) and control (n=100). Because we believe we will be able to accommodate up to 45 befrienders in each cycle, we anticipate recruiting up to 90 participants in total during each cycle (45 in the intervention and 45 in the control). If the first cycle does not recruit 68 participants, then there is no possibility of reaching our accrual target of 248 in three cycles. So, we propose a minimum of 68 participants with at least 55 people (80%) contributing outcome data at six months after randomisation for continuation. Similarly, if [service provider] cannot identify sufficient volunteers to facilitate telephone groups then there is no possibility of delivering the intervention.

On the basis of the pilot primary outcome data collected during the feasibility phase, the sample size for the main trial will be re-calculated, using the standard deviation, correlation and ICC from the pilot phase data and the minimum important difference of 8 points in mean SF-36 mental health scores used in the original sample size calculation. The sample size will either stay the same (if the SD of the primary outcome

is less than 20 points; correlation more than 0.50 and ICC less than 0.04) or increase (if the SD is more than 20 points; correlation less than 0.50, ICC more than 0.04). This will be done seven months after randomisation of the first cohort. Assuming the protocol and intervention remain unchanged, the participants recruited during the feasibility phase will be included in the full trial population. Processes will be included to try and identify the reasons for non response and numbers that were excluded due to factors such as language challenges.

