## 9. Statistics

### Sample Size

For the purposes of sample size estimation the primary outcome will be the mean SF-36 mental health (MH) dimension score at six-months post randomisation. The SF-36 mental health dimension is scored on a 0 (poor) to 100 (good health) scale. A previous general population survey of Sheffield residents has demonstrated that the SF-36 can successfully be used as an outcome measure for community dwelling residents aged 75 or more where a response rate of 82% was achieved (Walters et al 2001). From this general population survey of 3,084 Sheffield community residents, the mean SF-36 mental health score was 68.3 with a standard deviation of 19.9 (Walters et al 2001).

The developers of the SF-36 have suggested that differences between groups of between 5 and 10 points on the 100-point scale can be regarded as “clinically and socially relevant” (Ware et al 1993). If we assume a standard deviation of 20 points for the SF-36 Mental health score at six months post randomisation and that a mean difference in MH scores between the intervention and control group of 8 or more points is the smallest difference that can be regarded as clinically and practically important. We are going to analyse the six-month outcome data with a multiple regression/analysis of covariance model (ANCOVA) model with baseline score as a covariate. We shall assume a correlation of 0.50 between the baseline and six-month mental health score. Then to have an 90% power of detecting this 8-point mean difference in MH scores at six months between the Intervention and controls as statistically significant at the 5% (two-sided) level will require 99 patients per group (2 x 99 = 198 in total).

However, the telephone befriending intervention is a group or facilitator-led intervention. Therefore the success of the intervention may depend on the facilitator delivering it so that the outcomes of the participants in the same group with the same facilitator may be clustered. If we assume an average cluster size of 6 subjects per telephone befriending group and an intra cluster correlation (ICC) of 0.04, then the design effect is 1.28. With these assumptions and 99 subjects per group the power of the analysis is reduced to 80% to detect a mean difference of eight points in six-month MH scores. If 20% of participants drop out and are lost to follow-up then we will need to recruit and randomise 124 per group (248 in total).

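### The sample-size re-estimation thresholds leave most pilot results unassigned or at odds with the re-calculation, use an ICC from about six groups as a trigger, and set no maximum

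*Protocol*

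**What the plan says.** - **Pilot size** (section 3, Feasibility assessment). 90 people are randomised in the first wave. With 20% lost, "this will allow outcome measurement in 72 individuals to estimate a standard deviation for the primary outcome", together with the baseline to six-month correlation and the ICC.
- **Re-calculation** (section 3, Stopping rules). The new size uses the pilot SD, correlation and ICC with "the minimum important difference of 8 points in mean SF-36 mental health scores used in the original sample size calculation".
- **Decision** (same section). The size stays if the SD is below 20, the correlation above 0.50 *and* the ICC below 0.04, "or increase (if the SD is more than 20 points; correlation less than 0.50, ICC more than 0.04". The first list contains an explicit *and*; the second has only a semicolon and a comma. No maximum is given.
- **Capacity** (same section). "we anticipate recruiting up to 90 participants in total during each cycle", 45 per arm. A first cycle below 68 is said to put 248 out of reach in three cycles.
- **Planning values** (section 9, Sample Size). The authors "assume a standard deviation of 20 points for the SF-36 Mental health score at six months post randomisation", with correlation 0.50, six people per telephone group, ICC 0.04 and a stated design effect of 1.28. Before clustering, "to have an 90% power of detecting this 8-point mean difference in MH scores at six months" that is "statistically significant at the 5% (two-sided) level will require 99 patients per group (2 x 99 = 198 in total". Then "With these assumptions and 99 subjects per group the power of the analysis is reduced to 80" per cent. Dropout of 20% leads to 248.
- **Clustering** (section 9, Analysis of primary objective). Controls are clusters of size one, so only the intervention arm informs the ICC.
- **Timing** (Trial Summary). Wave 2 recruits in months 13-14, feasibility is assessed in month 18, and wave 3 recruits in months 19-20.
- **Contingency** (section 1, Risks and Benefits, Site recruitment). Other local branches would be approached if demand in waves 2 or 3 is too great. No number is given.

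**The concern.** The rule fixes the final recruitment target and has to be applied mid-trial, once outcome data have been seen. Two statisticians holding the same pilot data could reach different decisions, because most results have one or two favourable values and the text does not say what follows. Required size depends on the SD, correlation and ICC through a product, so a poor value of one can be offset by a good value of another; three separate cut-offs cannot express that. The ICC is the weakest of the three inputs, so chance in a handful of groups could move the target. Finally, an increase may call for more people than the planned cycles can take, and nothing says what happens then.

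**Working it through.** **1. The plan's own figure.** With SD 20 and r 0.50, SD²(1 - r²) = 400 × 0.75 = 300. At 90% power, n per arm = 2 × (1.960 + 1.282)² × 300/64 = 98.5, so 99. Then 99/0.8 = 123.75, so 124 per arm and 248 in total: reproduced. With design effect (DE) 1.28, power at 99 per arm is 81.9%, against the stated 80%. However, six per group and ICC 0.04 give DE = 1 + 5 × 0.04 = 1.20, for which power is 84.3%. A DE of 1.28 would need eight per group or an ICC of 0.056.

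**2. Formulas for the re-calculated total N.** Assumptions: 80% power (the re-calculation sentence does not restate it), six per group, 20% dropout, DE = 1 + 5 × ICC. Let n0 = 2 × (1.960 + 0.842)² × SD²(1 - r²)/64.
- Both arms inflated: N = 2 × n0 × DE/0.8.
- Intervention arm only inflated: N = 2 × n0 × (1 + DE)/2/0.8.
- 248 scaled: N = 248 × SD²(1 - r²)/300 × DE/1.20.

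**3. Which results the rule names.** Three quantities, each above or below its threshold, give 8 combinations; the rule clearly names 2. I simulated 40,000 pilots with the planning values true (six groups of six plus 36 controls). About 13% were all favourable, 8% all adverse and 79% mixed.

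**4. The 'any adverse value' reading.** Take SD 17, r 0.60, ICC 0.05. SD²(1 - r²) = 289 × 0.64 = 184.96, n0 = 45.4 and DE = 1.25.
- Intervention arm only: 2 × 45.37 × 1.125/0.8 = 128.
- Both arms: 2 × 45.37 × 1.25/0.8 = 142.
- 248 scaled: 248 × 184.96/300 × 1.25/1.20 = 159.

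All are far below 248, yet the ICC alone would trigger an increase. In about 43% of all simulated pilots the result is mixed while the scaled N is 248 or less.

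**5. Precision of the ICC.** 72 outcomes give about 36 in the intervention arm, and 36/6 = 6 groups. The ratio of between-group to within-group mean squares is distributed as (1 + 5ρ)/(1 - ρ) times F(5, 30), and the estimate is (ratio - 1)/(ratio + 5).
- True ICC 0.04 (multiplier 1.2/0.96 = 1.25): 95% sampling range -0.15 to 0.32.
- The estimate exceeds 0.04 when the ratio exceeds 1.25. The chance is about 31% at a true ICC of 0, 43% at 0.04 and 59% at 0.10.
- Eight groups of five change little: range about -0.17 to 0.31.

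**6. Capacity.** 248 - 2 × 90 = 68, so the 68-participant rule treats 90 per cycle as a ceiling. Three cycles hold 270, which is 22 above 248. If wave 1 recruits 68, then 68 + 180 = 248 and no room is left. The re-calculation follows wave 2, so wave 3 must absorb any increase.

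With the planning values true and negative ICC estimates set to zero, N exceeds 270 in about:
- 14% of pilots (intervention arm only inflated);
- 28% (both arms inflated);
- 37% (248 scaled).

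SD alone takes N past 270 at 20 × √(270/248) = 20.9 (248 scaled), about 22.2 (both arms) or about 23.2 (intervention arm only); the last two round up to whole people at each step.

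**The case against.** The strongest reply is that the Protocol already requires a joint re-calculation, and that the bracketed conditions only indicate the direction in which it will go. The choice between staying and increasing already implies a floor of 248. Both points are right. A reader might infer that the Protocol ignores how the three quantities combine; it does not. The fault is that the brackets then state a decision that can disagree with that calculation.

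A reader might also infer that the rule could leave the size unchanged with, say, SD 25, r 0.60 and ICC 0.03. The text does not support this: the 'stay' list is joined by an explicit *and*, so an SD of 25 cannot satisfy it. Such a pilot is either unassigned or, on the 'any adverse value' reading, an increase.

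Third, 270 is an anticipated capacity. Recruitment may extend to neighbouring boroughs and other branches may be approached, so it would be too strong to say that an increase is impossible. But no extra capacity is quantified, the timetable shows no fourth cycle, and the 68-participant rule depends on 90 being the limit.

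Last, how often 270 is passed depends heavily on the formula. Scaling 248 gives the highest figures because 248 already carries more than 80% power at a design effect of 1.20. That is why ranges are given here. It also shows that the formula has to be stated.

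**Conclusion.** The concern stands in this form. Mixed pilot results, about 79% if the planning values are true, are unassigned or ambiguous. If any adverse value triggers an increase, the thresholds contradict the Protocol's own re-calculation, as where about 128 to 159 people would do. An ICC from about six groups exceeds 0.04 in about 31% of pilots when there is no clustering at all, so it cannot act as a trigger. No maximum is named, although the planned cycles hold 270 and N passes that in about 14% to 37% of pilots with the planning values true.

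These figures assume 36 intervention outcomes in six equal groups, 80% power and 20% dropout. The documents do not support the stronger conclusions that the rule always gives the wrong target or that no increase could be recruited.

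**What to change.** In section 3 (Stopping rules):

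- Delete the three thresholds and let the joint re-calculation alone decide.
- State the formula, the power (80%), the cluster size, and whether one or both arms are inflated. Reconcile the design effect with section 9: six per group and ICC 0.04 give 1.20, not 1.28.
- Estimate SD and correlation from data pooled over arms. This also fits the stated blinding of the committees' statisticians, since group membership reveals allocation. Cost: a true 8-point difference would lift a pooled SD from 20 to √(400 + 16) = 20.4.
- Keep the planning ICC of 0.04 in the calculation. Report the pilot ICC descriptively, with sensitivity values.
- Keep 248 as the floor. Cap at what the remaining cycles can hold: the wave-1 number plus 180, at most 270 unless extra capacity is confirmed.
- If the calculation exceeds the cap, recruit to the cap and restate the power or the detectable difference.

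The cost is protocol wording, to be settled before pilot outcomes are seen. The downside is that a truly larger ICC would not raise the target, but six groups could not detect it reliably. Holding the ICC does not make the cap redundant: with 248 scaled, the upper quartile of the re-calculated N is still 270.

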## 5. Selection and withdrawal of participants

### Inclusion criteria

1. Aged 75 years or over;
2. Good cognitive function, defined as Six Cognitive Impairment Test (Brooke P, Bullock Ret al, 1999) score of 7 or under;
3. Living independently (including those who are co-resident with others) or in sheltered/ extra care housing;
4. Able to understand and converse in English.

### Exclusion criteria

1. Unable to use a telephone effectively with appropriate assistive technology;
2. In residential/ nursing care homes;
3. Already receiving telephone interventions.

Participants may withdraw from active participation in the study on request. Individuals removed from active participation in the intervention will not be replaced and will be followed up for all outcome information.

## 6. Randomisation and enrolment

Eligible participants will be randomised to one of the two arms by the trial manager or research assistant after receiving the consent form, via a centralised web based randomisation service provided through the Clinical Trials Research Unit (CTRU). The trial manager or research assistant will inform the individual and their general practitioner on the treatment allocation.

The randomisation sequence will be generated in advance by the trial statistician. There will be no stratification factors in the randomisation sequence.

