#### **Procedures required at six month follow-up**

Six month follow-up data will be collected by the Research Assistant (RA) via telephone. Follow up data will involve completion of the following;

- **SF-36 plus ONS wellbeing and telephone service cost questions (8)**
- **PHQ-9 (9)**
- **EQ-5D (10)**
- **GSE (11)**
- **de Jong Loneliness Scale (12)**
- **Health and Social Care Resource Use Questionnaire (13)**
- **SAE Checklist (17)**

We anticipate that 20% of participants will require assistance face-to-face. In these cases the RA will seek permission to visit the participant at home to administer the questionnaire (**essential documents 8-13 and 17**) face-to-face. Approximately 4 (5%) telephone calls (in each recruitment wave) will be recorded, with consent, for researcher training and monitoring purposes.

Some participants in the intervention arm will be invited to participate in a **semi-structured interview (16)** as part of the qualitative sub-study (see Section 10 below). An RA will ask permission to either visit the participants' home, or to telephone them to conduct the interview.

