## **11. Trial supervision**

The University of Sheffield will act as sponsor for the trial. Three committees will be established to govern the conduct of this study: the Trial Steering Committee (TSC), the Data Monitoring and Ethics Committee (DMEC) and the Trial Management Group (TMG). These committees will function in accordance with Sheffield CTRU standard operating procedures.

The TSC will consist of an independent chair with clinical and research expertise in the topic area, and two other topic experts as the sponsor sees fit and as agreed by the grant awarding body. The TSC will meet every 6 months from the start of the trial. The DMEC will consist of a neutral chair with research expertise, an independent statistician and an independent content expert. The DMEC will meet once before recruitment commences and every 6 months from the start of the recruitment. The DMEC can recommend premature closure of the trial to the TSC in accordance with Standard Operating Procedure GOV003.

A full time Trial Manager will contact the Chief Investigator and meet with the Assistant Director of the CTRU at weekly intervals while co-ordinating the trial. The TMG will meet at least at three-month intervals and will consist of: the Chief Investigator, the trial manager, the study statistician and a lay representative (from Sheffield Expert Elders or a similar organisation).

A Local Implementation Group will meet every two months and involve all local stakeholders, including members of the academic study team as well as representatives from charities, the NHS and the lay community.

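### The research assistant role may randomise, announce allocation and then administer the six-month SF-36, with nothing to mask it; who holds the sequence and computes the pilot ICC is also left open

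*Protocol*

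**What the plan says.** **Allocation.** Protocol Section 6: "Eligible participants will be randomised to one of the two arms by the trial manager or research assistant after receiving the consent form", using a central web service. The same section continues: "The trial manager or research assistant will inform the individual and their general practitioner on the treatment allocation". Section 8 (procedures before randomisation) likewise leaves randomisation to the research team, which records it on a study sheet.

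**Outcome collection.** Section 8 (six-month follow-up): "Six month follow-up data will be collected by the Research Assistant (RA) via telephone". The SF-36 is part of that interview. About 20% of participants are expected to need a home visit instead, also by an RA. The testing paragraph in Section 1 likewise has the researcher complete the SF-36 by telephone or at a visit.

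**Blinding.** Section 3 says of the steering committee and the TMG: "including their statisticians will be blind to treatment allocation whilst the trial is ongoing, but the trial manager and participants will not be blinded". RAs appear in neither list.

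**Statistician.** Section 6: "The randomisation sequence will be generated in advance by the trial statistician" and "There will be no stratification factors in the randomisation sequence". Section 11 gives the TMG's members as "the Chief Investigator, the trial manager, the study statistician and a lay representative". The stopping-rules text in Section 3 has the sample size re-estimated mid-trial from the pilot SD, correlation and ICC, and names nobody to do it.

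**The concern.** The SF-36 mental health score is subjective, and an interviewer obtains it from participants who know their arm. Participants cannot be masked, but the interviewer largely can be. An interviewer who knows the arm may prompt, probe or code differently between arms. That is a systematic error, and a larger sample does not remove it.

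Two features of the six-month contact add to the exposure. The SF-36 form also carries telephone-service cost questions, which may bring out the arm. Some intervention participants are also invited to a qualitative interview at this follow-up, and an RA asks their permission, so that RA must know the arm.

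The statistician's position is a separate matter. The TMG's statistician is meant to be blind while the trial runs. Anyone who has both an unstratified list and the order of randomisation can reconstruct the arms, and anyone who estimates the ICC by telephone group can see who is in the intervention arm.

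**Working it through.** **1. Tasks set side by side**

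| Task | Who | Where |
|---|---|---|
| Randomise | Trial manager or RA | Section 6; Section 8 (research team) |
| Tell participant and GP the arm | Trial manager or RA | Section 6 |
| Six-month SF-36 | RA, by telephone or visit | Sections 1 and 8 |
| Ask intervention participants about the qualitative interview | RA | Section 8 |
| Stated blind | Steering committee and TMG, with their statisticians | Section 3 |
| Stated not blind | Trial manager, participants | Section 3 |
| Blinding status of RAs | Not stated | – |

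The overlap is by role. No sentence assigns follow-up to an RA who took no part in that person's allocation, and none hides allocation at follow-up. Baseline measures are taken before randomisation, so the exposure is confined to the follow-up interviews.

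**2. Statistician and ICC.** Section 6 speaks of the trial statistician and Section 11 of the study statistician. The protocol neither equates nor distinguishes them. Telephone groups exist only in the intervention arm, and Section 9 treats controls as clusters of size one, so the cluster variable shows the arm. Section 13 withholds identifiable data from the statistician, but neither the cluster variable nor the randomisation order identifies a person by name.

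**3. The plan's own figure, for scale.** Inputs from Section 9: SD 20, baseline correlation 0.50, difference 8, two-sided 5%, power 90%.

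- Residual SD = 20 × √(1 − 0.50²) = √300 = 17.32.
- n per arm = 2 × [17.32 × (1.960 + 1.282) / 8]² = 98.5, so 99. This reproduces.
- 99 / 0.8 = 123.75, so 124 per arm and 248 in total. This reproduces.

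**4. Standard error of the difference, 99 analysed per arm.** A group size of 6 and an ICC of 0.04 give 1 + 5 × 0.04 = 1.20. The protocol prints 1.28, which is a separate matter.

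- Baseline-adjusted, 1.20 in both arms: √(300 × 2.4 / 99) = 2.70.
- Baseline-adjusted, 1.28 in both arms: √(300 × 2.56 / 99) = 2.79.
- Unadjusted, 1.20 in the intervention arm only: √(400 × 2.2 / 99) = 2.98.

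**5. Illustrative effect of an assessor shift b when there is no true effect.** Rejection probability = 1 − Φ(1.96 − b/SE) + Φ(−1.96 − b/SE). The values of b are assumed; no document gives one.

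| b (points) | SE 2.70 | SE 2.98 |
|---|---|---|
| 0 | 5.0% | 5.0% |
| 1 | 6.6% | 6.3% |
| 2 | 11.5% | 10.3% |
| 3 | 19.9% | 17.2% |

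Adjusting for baseline with the design effect in the intervention arm only gives SE = √(300 × 2.2 / 99) = 2.58 and rates of 6.7%, 12.1% and 21.3%, so the picture hardly depends on this choice.

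**The case against.** Several points on the other side are sound.

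- **No RA blind is claimed.** A reader might infer that the task assignments break a promised blind. They do not: Section 3 promises blinding only for the two committees and their statisticians. For RAs the fault is a missing safeguard and silence about their status.
- **The overlap is by role.** The text does not say that an RA follows up the people whom that RA randomised. It also does not prevent it.
- **Independent completion is mentioned.** Section 1 allows follow-up forms to be completed by the participant alone. The same paragraph then gives the SF-36 to the researcher, as Section 8 does, so this is little protection.
- **Some calls are recorded.** About 5% per wave are recorded for training and monitoring. That helps consistency but masks nobody.
- **The trial manager is a stated exception.** It is tempting to call it a contradiction that the TMG is blind yet contains the unblinded trial manager. The same sentence makes that exception, so at most the wording needs tidying.
- **Custody of the sequence is not stated.** Generating a list is not the same as keeping it or seeing each participant's arm. Allocation is released by a central web service. Nor does the protocol say that the TMG statistician will handle interim outcomes or compute the ICC. A breach is therefore not shown; what stands is that the text does not rule one out.
- **Re-estimation does not use the treatment effect.** It uses fixed thresholds for SD, correlation and ICC and can only keep or raise the sample size, so the scope for harm from that step is limited.
- **The bias sizes are assumed.** They show scale and are not evidence that bias will occur.

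What survives is the unprotected outcome interview, plus a need to clarify the statistician's position.

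**Conclusion.** The point holds in this limited form. As written, the protocol allows the role that knows and announces allocation to administer the subjective primary outcome, with no separation of staff and no masking. That leaves open an avoidable source of assessor bias. The sample size is unaffected.

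The statements about the TMG statistician conflict only if that person generates and keeps the sequence or computes the by-group ICC. The document does not exclude either, and neither should be read as established. Blinding of the steering committee is not touched by the RAs' tasks.

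No size of bias can be taken from the documents. Under assumed shifts of 1, 2 or 3 points, the nominal 5% error rate becomes about 6–7%, 10–12% or 17–20% for standard errors of 2.7 to 3.0. This is a cheap improvement to make before the first six-month interviews, because masking lost at an interview cannot be restored afterwards.

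**What to change.** 1. **Sections 6 and 8 (before randomisation):** assign randomisation and allocation letters to the trial manager, who is already unblinded, and remove RAs from both tasks.
2. **Section 13:** use the database's existing privilege controls to hide allocation from RAs who do follow-up.
3. **Section 8 (follow-up):** ask the SF-36 before the telephone-cost and resource-use questions. Have the trial manager, or someone other than the outcome assessor, make the qualitative-interview invitation; Section 10.2 already gives that interview to the trial manager or content expert. Have the RA record any unmasking and when it occurred.
4. **Section 3:** state that follow-up RAs are to be masked and that the trial manager is the TMG's unblinded member.
5. **Sections 3 and 6:** state that the sequence and the by-group pilot ICC are kept from the TMG statistician. For example, a unit statistician outside the TMG could generate and hold the sequence, and the statistician already on the data monitoring committee could compute the ICC and report only that value.

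The cost is protocol wording, a change in database access, and more work for the trial manager. No new staff are needed and the sample size does not change. Some participants will still reveal their arm, which is why unmasking should be recorded.
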